9.1.3 Acute Assessment Units (AAUs)

Patients who present to AAUs are typically referrals from GP practices. In this setting, the process will follow that of the Emergency Department setting.

9.1.4 Hospitalised patients (admitted for any reason other than COVID-19) who subsequently test positive for COVID-19

Following admission to hospital, should a patient subsequently test positive for COVID-19, hospital teams will contact the research team (if different to the hospital team) to notify them of a possible patient. The hospital / research team will inform and consent the patient as well as coordinate the screening assessments. Patients consented in this setting and confirmed eligible will be randomised in the hospital and subsequent visits can either be performed face to face, if feasible, by the research / hospital team or via video / phone calls according to the protocol. For patients recruited while in hospital, all assessments will be performed and camostat will be given by the hospital staff (if the patient is randomised to camostat) and their routine hospital care will not be affected while participating in the trial. If patients wish to do so, they can use the Medidata patient application ('app') in addition to the diary card and app instructions and consent form can be provided.

9.2 Informed Consent

Written and/or verbal versions of the ICD will be presented to the patients detailing the exact nature of the trial; what it will involve for the patient; the implications and constraints of the protocol; and any risks involved in taking part. It will be clearly stated that the patient is free to withdraw from the study at any time for any reason without prejudice to future care, without affecting their legal rights, and with no obligation to give the reason for withdrawal.

Given the acute nature of COVID-19 and the potential for rapid progression of symptoms, patients will be given sufficient time to consider their decision.

Wherever possible the patient will be provided with a copy of the ICD in a paper format. If paper is not permitted, an electronic version of the ICD will be provided that the clinical research team will go through with the patient either in person or over the telephone or video link.

In whatever way the information is presented, the patient must be given adequate time to think about their commitment to the trial and to allow them to ask any questions about the trial.

The patient may provide verbal consent under the current restrictions and be asked to sign a copy of the ICD (at the earliest opportunity) to be made available at a later date to the research team (this could take the form of a photograph which is sent to/taken by the clinical trial team). This consent in whichever form must be documented fully by the person taking consent and the person taking consent should sign a consent form also. Reconciling the two consent forms will take place later once restrictions are lifted, or if this is not possible, the documentation in the patient's records will serve to show that consent had been obtained and the way in which consent was obtained. The notation in the patient's record should also include a statement of why the ICD signed by the patient was not retained e.g. due to potential contamination of the document by infectious material).

It is acknowledged that usual research practice is for the researcher and the patient to both sign and date the same ICD, in person when together. However, given the nature of the COVID-19 outbreak and to minimise avoidable risks, the preceding process has been agreed and providing careful and thorough documentation, consent can be taken in this way. The patient's GP will be made aware of their participation in the trial via letter.

Patients who choose to use the Medidata patient app in addition to the diary card will be asked to sign a separate consent, covering data protection and instructions, for use of the app. Management of this consent will be the same as for the main trial consent.

10 DEFINITION OF END OF TRIAL

It is the responsibility of the Sponsor to inform the MHRA and the REC within 90 days of the End of Trial (EoT) that the trial has closed.

In cases of early termination of the trial (for example, due to toxicity) or a temporary halt by the CDD, the CDD will notify the MHRA and the REC within 15 days of the decision and a detailed, written explanation for the termination/halt will be given.

Recruitment will cease when:

- Camostat is considered too toxic to continue before the required number of patients have been recruited.
- The stated number of patients to be recruited has been reached.
- The stated objectives of the trial are achieved.
- The stated objectives of the trial are unlikely to be met based on emerging data from camostat trials worldwide, and it is confirmed the trial is to stop due to futility (end of trial will be the date of this decision).
- The stated objectives of the trial are likely to be met based on emerging data from camostat trials worldwide, and it is confirmed the trial is to stop due to efficacy proven elsewhere (end of trial will be the date of this decision).

Regardless of the reason for termination, all data available for patients at the time of discontinuation of follow-up must be recorded in the electronic/case report form (e/CRF). All reasons for discontinuation of treatment must be documented.

In terminating the trial, Investigators must ensure that provision is made to ensure appropriate ongoing care for the patient.

The End of Recruitment is defined as the date the last patient is recruited.

The End of Trial is defined as the date when the Day 28 data has been obtained for the last patient or the final follow-up visit or, if the trial is closed due to emerging data from camostat trials worldwide, the date of the Sponsor's decision to close the trial (whichever is the latter).

For analysis and reporting plans, please see Section 13.

To note: If camostat related SAEs are still ongoing at the EoT point, these will continue to be followed up as per protocol.

11 DISCONTINUATION/ WITHDRAWAL OF PATIENTS FROM STUDY TREATMENT

Each patient has the right to withdraw from the trial at any time. In addition, the investigator may discontinue a patient from the trial at any time if the investigator considers it necessary for any reason including:

- Ineligibility (identified retrospectively).
- Significant protocol deviation.
- Significant non-compliance with treatment regimen or trial requirements.
- Consent withdrawn*.

The reason for withdrawal will be recorded in the patient's records and e/CRF. In the case of a patient being withdrawn from the trial, attempts will be made to recruit a replacement.

*A decision by a patient that they no longer wish to continue receiving trial treatment should not be considered to be a withdrawal of consent for follow-up. However, patients are free to withdraw consent for some or all aspects of the trial at any time if they wish to do so. In accordance with regulatory guidance, de-identified data that have already been collected and incorporated in the trial database will continue to be used (and any identifiable data will be destroyed).

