5.3.4 Day 7 visit

It is intended that the Day 7 interaction with the patient is made by a clinical professional who can assess whether the patient has recovered. Patients may be visited at home on Day 7 (to collect research bloods and [REDACTED] as well as receiving the daily video (phone) call. If at this visit/during the call, it is assessed that the patient (on the treatment arm) has recovered, the patient may be asked to discontinue with camostat administration, and the drug will be disposed of as per an approved process. Follow up calls and visits as per protocol will continue.

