8.3.4 Days 1-28

Review of hospital and primary care records to evaluate use of any form of supplementary oxygen, CXR/ CT reports or images to assess progression or evolution of pneumonia and evidence of pulmonary thromboembolic events plus documentation of death (COVID-19 related mortality) during trial period.

Patients who are hospitalised will be followed up following discharge. The Day 28 visit can be done up to 28 days post discharge if the patient was hospitalised at the time of day 28.

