12.3 Procedures for Recording Adverse Events

All AEs will be recorded in the eCRF.

The following information will be recorded: patient ID including the patient trial number, age and gender; verbatim term for the AE description, date of onset and end date as well as outcome, severity of the event, assessment of relatedness to trial medication, other suspect drug or device and action taken. Follow-up information should be provided as necessary. AEs should be recorded on the CRF from the date of written/verbal informed consent (whichever is the earlier) being given until they have completed the 28 days from Day 1 follow up period.

AEs considered related to the trial medication or COVID-19, as judged by a medically qualified investigator or the sponsor will be followed until resolution or the event is considered stable. All related AEs that result in a patient's withdrawal from the trial or are present at the end of the trial, should be followed up until a satisfactory resolution occurs.

It will be left to the investigator's clinical judgment whether or not an AE is of sufficient severity to require the patient's removal from treatment. Although the Sponsor will hold the final decision if there is a disagreement in the management of the patient's treatment. A patient may also voluntarily withdraw from treatment due to what he or she perceives as an intolerable AE. If either of these occurs, the patient must undergo an end of study assessment and be given appropriate care under medical supervision until symptoms of the AEs cease or the condition becomes stable.

The severity of events will be assessed on the following scale: 1 = mild, 2 = moderate, 3 = severe and as judged by a medically qualified investigator.

For hospitalised patients who are admitted (for any reason other than COVID-19) and subsequently test positive for COVID-19, medical occurrences or symptoms of deterioration that are expected as a consequence of the participant's admission hospital should be recorded in the patient's medical notes and only be reported as AEs in the eCRF if medically judged to have unexpectedly worsened during the study. AEs considered related to the trial medication or COVID-19, as judged by a medically qualified investigator or the sponsor will be reported in the eCRF.

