11.1 Populations

The efficacy population will only include patients from the camostat arm where they have completed 5 days of treatment and in the control arm where they have completed 14 days of treatment or reached an endpoint (eg hospitalisation). All primary and secondary analyses will be conducted with this population. An intention-to-treat analysis of the main secondary outcomes (COVID-19 related hospital admissions, supplementary oxygen-free days, ventilator-free days, time to worst point on the 9-point ordinal scale) will also be conducted, should the data allow.

Patients who agree to the taking of blood samples will be included in the analysis of the PK data. The mean and SD will be reported at each time point (Days 7 and 14), as will the mean changes. The data may be log (or other) transformed if not normally distributed. [REDACTED]

[REDACTED] Change will be
change from previous blood test.

The safety population will include all patients with at least one dose of treatment (camostat or control). Safety data will be collected from the date of written consent. Safety variables will be summarised by descriptive statistics.

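### Protocol section 11 lets the investigator take a randomised patient out of the trial, and no text keeps that patient in follow-up to Day 28

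*Protocol*

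**What the plan says.** Protocol section 11 is headed as a section on withdrawal from study treatment, but its operative sentence concerns the trial: "the investigator may discontinue a patient from the trial at any time if the investigator considers it necessary for any reason including" four listed grounds. One of these is "Significant non-compliance with treatment regimen or trial requirements". The section continues: "In the case of a patient being withdrawn from the trial, attempts will be made to recruit a replacement".

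Follow-up after stopping is addressed in three places, each for a different situation:

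- The section 11 footnote: "A decision by a patient that they no longer wish to continue receiving trial treatment should not be considered to be a withdrawal of consent". The consent in question is to being followed up. This concerns the patient's own choice.
- Protocol 5.3.4, where camostat is stopped at Day 7 because the patient has recovered: "Follow up calls and visits as per protocol will continue".
- Protocol 12.3, after removal from treatment because of an adverse event: "the patient must undergo an end of study assessment and be given appropriate care under medical supervision". The timing of that assessment is not tied to Day 28.

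Protocol 8.3.4 schedules over Days 1-28: "Review of hospital and primary care records to evaluate use of any form of supplementary oxygen", together with imaging and deaths. It does not say whether this review goes on after an investigator has withdrawn a patient.

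On analysis, SAP 11.1 runs the primary and secondary analyses on the efficacy population. An intention-to-treat analysis of four secondary outcomes "will also be conducted, should the data allow". SAP 11.2 expects about 5% missing data and plans sensitivity analyses, including multiple imputation under missing at random. Neither document says how replaced patients or their replacements are analysed.

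**The concern.** Stopping a treatment and leaving a trial are different events, and only the second ends data collection. If section 11 is applied as worded, a patient withdrawn for non-compliance may have no further calls, adverse event questions or record checks.

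The loss could well depend on outcome. Poor tolerability or worsening illness can each lead to missed doses. The investigator knows the arm and has an unrestricted discretion. Only camostat patients have a dosing regimen to breach (four fasted doses a day, Protocol 7.2.5), and SAP 6.5 lists compliance for that arm alone.

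Two things are at stake. The first is the between-arm description of admission, oxygen use, ventilation and the ordinal scale, which is meant to inform later trials. The second is the primary safety objective, because adverse events are to be recorded for 28 days from Day 1. Protocol 12.3 secures follow-up of related events that led to withdrawal, but not detection of events that start later.

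**Working it through.** **The plan's own figure.** Protocol 13.2 gives a recruitment rate of 50%, 95% CI 43% to 57%, standard error 3.5%. The denominator is patients approached: 100/0.5 = 200. SE = sqrt(0.5 × 0.5/200) = 3.54%, and 50% ± 1.96 × 3.54% = 43.1% to 56.9%. The figure reproduces. It contains no input for dropout or replacement, so it does not bear on this point.

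**Does any text cover the investigator's withdrawal?**

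- Patient chooses to stop treatment: follow-up protected (section 11 footnote).
- Camostat stopped for recovery: follow-up continues (5.3.4).
- Removal from treatment for an adverse event: an end-of-study assessment, with Day 28 not stated (12.3).
- Investigator withdraws the patient for non-compliance, deviation or late-found ineligibility: no statement.

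The SAP treats the two events as distinct. Table 7 has separate columns for withdrawal of the drug and withdrawal from the study. Table 2 lists withdrawal by the investigator apart from the row that marks follow-up as still allowed for control patients.

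**Size.** The documents give neither a withdrawal rate nor an admission rate, so the numbers lost and the event rates below are assumptions. Let k camostat and m control patients be unobserved to Day 28, with 50 per arm. The camostat admission proportion is then known only to within k/50 and the control proportion to within m/50. The best-to-worst bounds on the difference are (k + m)/50 wide:

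- k + m = 1: 1/50 = 2 percentage points
- k + m = 5 (the SAP's 5% of 100): 5/50 = 10 points
- k + m = 10: 10/50 = 20 points

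For scale, the standard error of the difference with 50 per arm is sqrt(2p(1 − p)/50): 4.4 points at p = 5%, 6.0 at 10% and 8.0 at 20%.

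**Effect of replacement.** Suppose replacement restores 50 observed patients per arm and all randomised patients stay in the denominator. The width becomes k/(50 + k) + m/(50 + m). For k = 5, m = 0 it is 5/55 = 9.1 points; for k = 10, m = 0 it is 10/60 = 16.7 points.

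**Bias.** Suppose retained camostat patients have a 10% admission rate and withdrawn ones 20% to 40%. An analysis that gives the withdrawn patients the retained rate understates the camostat rate by (k/50) × (withdrawn rate − 10%):

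- k = 5: 1.0 to 3.0 points (0.9 to 2.7 with replacement, using 5/55)
- k = 10: 2.0 to 6.0 points (1.7 to 5.0 with replacement, using 10/60)

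Replacement restores the count and hardly changes the bias.

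**Balance between arms.** An overall 5% fits 3 camostat and 2 control patients lost (3/50 = 6% and 2/50 = 4%) as well as 5 and 0 (10% and 0%). The SAP's overall figure therefore says nothing about asymmetry.

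**The case against.** The strongest reply is that no passage says data collection stops. The section heading speaks of study treatment. Record review over Days 1-28 names no exception for withdrawn patients, SAE collection runs for 28 days from Day 1 (Protocol 12.5), and the synopsis asks teams to make every effort to stay in contact with any randomised patient hospitalised for COVID-19 within 28 days. Three of the four intention-to-treat outcomes (admission, oxygen, ventilation) could come from records. Multiple imputation is planned, no significance testing is done, and one dose is enough to stay in the safety population.

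Much of this stands. It makes the point an open gap rather than a stated loss, and it limits the impact. It does not close the gap, because none of these passages says that it applies after an investigator has withdrawn the patient. Ordinal scale status is collected at the calls (8.3.1, 8.3.3), and the daily calls are also where adverse events are assessed (5.3.2). Imputation under missing at random fails if withdrawal depends on the unobserved outcome.

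A reader might infer three stronger claims that the documents do not support:

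- That replacement conceals the loss. SAP Table 2 reports withdrawals by arm and reason on the full analysis population, which is all enrolled patients except those enrolled in error before treatment. Exclusions from the efficacy analysis are listed, and participant flow is shown by arm.
- That replacement fills the camostat arm with compliant patients. Randomisation is 1:1 through the web system, and nothing assigns a replacement to the vacated arm or selects for compliance.
- That the losses must be one-sided. Trial requirements, ineligibility and protocol deviations apply to both arms.

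**Conclusion.** The gap is real. An investigator may withdraw a randomised patient from the trial, and no text secures that patient's outcomes and adverse events to Day 28. A conditional intention-to-treat analysis cannot supply data that were not collected, and imputation under missing at random is only a partial remedy.

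How much it matters depends on how often the power is used, which the documents do not say. Five patients unobserved would leave bounds on the admission difference wider than its standard error at any of the admission rates tried (10 points against 4.4 to 8.0). A heavier loss on camostat is plausible but remains an inference. The consequences are moderate, since the trial is descriptive and the efficacy outcomes are secondary. The change is still worth making because it costs so little.

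**What to change.** Add to Protocol section 11 that any randomised patient, in either arm, who is withdrawn by the investigator:

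- stays in the scheduled calls, adverse event collection and hospital and primary care record review to Day 28, unless the patient withdraws consent for these; and
- stays in the all-randomised (intention-to-treat) analysis in the assigned arm, whether or not a replacement is recruited.

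State also that replacements are randomised as new patients and counted as additional to those they replace. SAP 11.1 should carry the same two analysis rules.

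The wording should be about follow-up, so that it works for control patients, who have no study drug to stop. It changes no rule on stopping treatment. Replacement need not be deleted, since it barely alters the bias. The calls and record review are already scheduled, so the cost is a wording amendment and a few more calls and record checks.

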12 SAFETY REPORTING

12.1 Definitions

12.1.1 Adverse Event (AE)

An AE or adverse experience is:

An adverse event (AE) is any untoward, undesired or unplanned medical occurrence in a patient administered an investigational medicinal product (IMP), a comparator product or an approved drug.

An AE can therefore be any unfavourable and unintended sign (including an abnormal laboratory finding), symptom or disease temporally associated with the use of the trial medication, whether or not considered related to the trial medication.

AEs should be reported for all patients regardless of which arm they were randomised to.

12.1.2 Adverse Drug Reaction (ADR)

All untoward and unintended responses to a medicinal product related to any dose.

The phrase "responses to a medicinal products" means that a causal relationship between a trial medication and an AE is at least a reasonable possibility, i.e., the relationship cannot be ruled out.

All cases judged by either the reporting medically qualified professional or the sponsor as having a reasonable suspected causal relationship to the trial medication qualify as adverse reactions.

12.1.3 Serious Adverse Event (SAE)

A serious adverse event is any untoward medical occurrence that at any dose:

- Results in death
- Is life-threatening, NOTE: A "life-threatening" event is defined as an event when the patient was at substantial risk of dying at the time of the AE occurring; it does not refer to an event which hypothetically might have caused death if it were more severe.
- Requires in-patient hospitalisation where they are admitted for more than 24 hours or prolongs existing in-patient hospitalisation (although some hospitalisations are exempt from SAE reporting, i.e. hospital admissions planned prior to the patient entering the trial; overnight stays for planned procedures). NOTE: if a patient is in hospital when they sign informed consent to participate in the trial, any event after consent that would have resulted in hospitalisation, or any event that prolongs the existing in-patient hospitalisation should be reported as serious.
- Results in persistent or significant disability/incapacity, or
- Is a congenital anomaly/birth defect.
- Other important medical events. NOTE: A medically important event is defined as any event that may jeopardise the patient or may require intervention to prevent one of the outcomes listed above. Examples include allergic bronchospasm (a serious problem with breathing) requiring treatment in an emergency room, serious blood dyscrasias (blood disorders) or seizures/convulsions that do not result in hospitalisation. Development of drug dependency or drug abuse including overdose would also be examples of important medical events. Other events that may not result in death, are not life threatening, or do not require hospitalisation, may be considered a serious adverse event when, based upon appropriate medical judgement, the event may jeopardise the patient and may require medical or surgical intervention to prevent one of the outcomes listed above.

To ensure no confusion or misunderstanding of the difference between the terms "serious" and "severe", which are not synonymous, the following note of clarification is provided:

The term "severe" is often used to describe the intensity (severity) of a specific event (as in mild, moderate, or severe myocardial infarction); the event itself, however, may be of relatively minor medical significance (such as severe headache). This is not the same as "serious," which is based on patient/event outcome or action criteria usually associated with events that pose a threat to a patient's life or functioning as defined in the bullet points above. Seriousness (not severity) serves as a guide for defining regulatory reporting obligations.

